## 2.4.2 Secondary Endpoints

- Recurrent hernias (functional hernias) requiring surgical intervention
- True recurrence at 24 months
- Evidence of Eventration/Hernia Recurrence (Radiographic)
- Fluid collection (Seroma, Hematoma)
- Surgical Site Infections
- Systemic Infections
- Enterocutaneous Fistula
- Dehiscence
- Implant failure requiring partial or total removal
- Patient satisfaction (using the SF-36 questionnaire) at Baseline, 3 months, 6 months, 12, and 24 months.
- Days to discharge
- Pain measured using the Visual Analog Scale for discomfort at Baseline, 3 months, 6 months, 12 months, and 24 months.
- Patient contentment with the cosmetic results at 12 months, 24 months and/or at the time of study withdrawal except for patients who have been withdrawn due to recurrence.

# 2.4.3 Safety Endpoints

- Type of Adverse Events (volunteered and elicited).
- Frequency of Adverse Events (volunteered and elicited).

#### III. Statistical Design

This study is a single-center prospective, randomized study evaluating Fortiva Porcine Dermis vs. Strattice Reconstructive Tissue Matrix in complex hernia repair. Up to 120 total subjects will be randomized in a 1:1 ratio.

## 3.1 Sample Size

Patients will be randomized at a 1:1 ratio. A total of 120 patients, 60 Strattice and 60 Fortiva patients will be enrolled. This sample size will give the study a 95% significance level and 80% power and shall provide preliminary data and benchmark evidence for direct comparison of two post-market biologic mesh materials when used as reinforcement in large abdominal hernias. The analysis also contemplates a 15 to 20% dropout rate for the primary outcome.

Power analysis and sample size determination is based on Log-rank test for equality of recurrence rates over time during the study between groups. The hazard rates of recurrence are key quantities. Often the hazard rates are very hard to obtain. However, based on the mathematical relationships of hazard function and recurrence function, we can derive the hazard rate from either of two related quantities which are

often reported in literature –(1) the proportion of recurrence-free during the study period or (2) median recurrence-free time, from Kaplan-Meier product limit survival curve.

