#### 2.4 Study Endpoints

## 2.4.1 Primary Endpoints

The primary objective of this study is to compare the incidence of true hernia recurrence (true defect in the implant repair in which intra-abdominal contents are protruding through the defect) at or before 1 year between the Fortiva™ Porcine Dermis group compared with Strattice™ Reconstructive Tissue Matrix group.

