#### 3.2 Statistical Plan

Given the 1:1 randomized nature of the clinical trial and to preserve the inherent characteristics of the randomization, analysis by intention-to-treat (ITT) is chosen. This type of analysis compares the study groups in terms of the treatment to which they were randomly allocated, irrespective of the treatment they actually received or other trial outcomes. Regardless of protocol deviations and participant compliance or withdrawal, analysis is performed according to the assigned treatment group. This type of analysis will also help to demonstrate if there is superiority of one mesh over the other.

If there is no superiority of one mesh over the other, analysis will be performed using the same outcomes to assess if there is equivalence between both meshes. This will demonstrate that there is no clinically significant difference between the two treatment arms.

For statistical analysis, these outcomes can be classified into two measurement scales- continuous and categorical. For continuous outcome, mean and standard deviation, median and range for each group will be calculated. ANOVA will be used to compare the difference in the means among the two groups when data are reasonably normally distributed. Otherwise, non-parametric ANOVA will be used. For categorical data, proportion will be obtained for each outcome, along with 95% CI derived from exact method. Difference in the proportions among the four groups will be compared using Fisher's exact test.

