## 3.3 Study Population

The study involves consenting adults 18 years of age and older with a large, complex abdominal wall hernia. The specific definition of this population is described in the Inclusion/Exclusion criteria.

Given the 1:1 randomized nature of the clinical trial and to preserve the inherent characteristics of the randomization, analysis by intention-to-treat (ITT) is chosen. This type of analysis compares the study groups in terms of the treatment to which they were randomly allocated, irrespective of the treatment they actually received or other trial outcomes. Regardless of protocol deviations and participant compliance or withdrawal, analysis is performed according to the assigned treatment group. This type of analysis will also help to demonstrate if there is superiority of one implant over the other.

If there is no superiority of one implant over the other, analysis will be performed using the same outcomes to assess if there is equivalence between both implants. This will demonstrate that there is no clinically significant difference between the two treatment arms.

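### The 80% power in Section 3.1 is for a log-rank test, but Section 3.2 plans no time-to-event analysis and offers only Fisher's exact test for the 1-year recurrence endpoint

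*Combined protocol and SAP*

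**What the plan says.** Section 3.1 sets 120 patients, 60 per arm, and states: "This sample size will give the study a 95% significance level and 80% power". On the method it says: "Power analysis and sample size determination is based on Log-rank test for equality of recurrence rates over time during the study between groups". It explains that hazard rates can be derived from a recurrence-free proportion or a median recurrence-free time, but gives no value for either. On losses: "The analysis also contemplates a 15 to 20% dropout rate for the primary outcome". It does not say whether 120 already allows for them. It adds that the sample "shall provide preliminary data and benchmark evidence".

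Section 2.4.1 makes the primary objective a comparison of the incidence of true hernia recurrence "at or before 1 year between the Fortiva" and Strattice groups. Section II likewise gives the primary outcome as recurrence at 1 year.

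Section 3.2 says that "these outcomes can be classified into two measurement scales- continuous and categorical". Continuous outcomes get ANOVA or a non-parametric version. Categorical outcomes get proportions with exact 95% confidence intervals, and then: "Difference in the proportions among the four groups will be compared using Fisher's exact test". Section 3.3 repeats the intention-to-treat and equivalence text, including "This type of analysis will also help to demonstrate if there is superiority of one implant over the other", and names no test.

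**The concern.** The power claim and the analysis plan describe different analyses. A log-rank test compares the whole recurrence-free curves and uses partial follow-up from patients who leave early. Fisher's test compares two proportions, so each patient who leaves before 12 months must be either dropped or given a status, and the plan does not say which.

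A reader therefore cannot tell which test decides the primary endpoint, or what difference 60 per arm can detect. This matters more than usual here because Sections 3.2 and 3.3 send a non-significant superiority result on to an equivalence assessment. A null result would be read as coming from an 80%-powered comparison, when that figure belongs to a test missing from the plan.

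**Working it through.** **1. The plan's own figure.** The power of a log-rank test follows from the number of events and the hazard ratio. Section 3.1 gives neither, nor the rates from which to derive them. The 80% cannot be reproduced. The horizon is also open: 3.1 speaks of recurrence during the study, which runs to 24 months, although it ties dropout to the primary outcome, which points to 12 months.

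**2. The sections side by side.**
- Power basis (3.1): log-rank, time to event.
- Endpoint (2.4.1): incidence at or before 1 year.
- Test available for that endpoint (3.2): Fisher's exact, worded for four groups in a two-arm trial.
- Log-rank and Kaplan-Meier methods appear only in 3.1, for sizing.

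**3. Illustration of the difference.** From the plan: 60 per arm and 15 to 20% dropout. Assumed: two-sided 5%, exponential recurrence and dropout, 12-month horizon, recurrences before dropout kept. One arm is set at 18% or 50%, the ends of the general incisional-hernia range in Section 2.2; these are not 12-month rates for these devices. The other arm's rate was solved so that the log-rank test has about 80% power. Both tests were then run on the same simulated trials (20,000 per row, standard error about 0.3 points).

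| Rates, dropout | Log-rank | Fisher, evaluable | Fisher, dropouts counted as recurrence-free |
|---|---|---|---|
| 18 vs 41.8%, 15% | 80.5 | 75.9 | 72.9 |
| 18 vs 42.0%, 20% | 80.1 | 74.7 | 71.7 |
| 18 vs 2.7%, 15% | 80.5 | 73.0 | 68.1 |
| 18 vs 2.6%, 20% | 80.4 | 72.6 | 67.5 |
| 50 vs 25.2%, 15% | 78.8 | 73.6 | 69.9 |
| 50 vs 24.9%, 20% | 78.6 | 73.2 | 69.5 |
| 50 vs 74.3%, 15% | 80.6 | 71.8 | 68.7 |
| 50 vs 74.5%, 20% | 80.4 | 70.4 | 67.5 |

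Fisher on evaluable patients is about 5 to 10 points below log-rank. If dropouts are counted as recurrence-free (one possible rule, not stated in the plan), it is about 8 to 13 points below.

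**4. Check on the first row.** The hazard ratio at 18 vs 42% is ln(0.58)/ln(0.82) = 0.545/0.198 = 2.7. Schoenfeld's formula needs 4 × (1.96 + 0.84)² / (ln 2.7)² events, which is 31 before rounding the hazard ratio. Expected events per arm are 60 × λ/(λ+μ) × (1 − e^−(λ+μ)), where λ is the recurrence hazard and μ the dropout hazard. At 15% dropout μ = −ln(0.85) = 0.163. With λ = 0.198 this gives 10.0, and with λ = 0.541 (41.8%) it gives 23.3, about 33 in total. That agrees with power near 80%.

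**5. Where the gap comes from.** At 18 vs 18% with 17.5% dropout, the type I error is 5.0% for log-rank and 3.7% for Fisher. An uncorrected chi-square test on the same evaluable patients comes within 0 to 2 points of log-rank in three of the four cases (18 vs 42%: 79.1 against 80.4; 18 vs 2.7%: 80.4 against 80.3). At 50 vs 74% it is 5 to 6 points below. There the Fisher gap is 8.8 to 10.0 points, so conservatism explains only about 4 (8.8 − 5, or 10.0 − 6). Elsewhere it explains most or all of the gap.

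**6. On the rate scale.** Fisher on evaluable patients reaches 80% at 18 vs 43.1–43.6%, 18 vs 1.8–2.0%, 50 vs 23.4–23.9% and 50 vs 76.7–77.4%. Against the table, that is about 1 to 3 percentage points further out. The two tests disagree on significance in about 6 to 7% of simulated trials at 18 vs 42% and at 50 vs 25%.

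**The case against.** The strongest reply is that the difference is small and rests on assumed rates. The rates come from a general background range with no stated horizon, and the second arm was solved to hit 80%. The gap also depends on the sizing formula. Without dropout, at pairs of rates where Freedman's formula gives 80%, Fisher has 77 to 79%. At Schoenfeld's 80% pairs it has 65 to 73%, partly because that formula is optimistic at extreme hazard ratios. Section 3.1 also calls the data preliminary. All of this limits the size of the point. It does not remove the mismatch, because the plan still makes a numerical power claim and aims at superiority and then equivalence.

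Three stronger readings are tempting, and the documents support none of them:
- **That the trial has less than 80% power, or that 3.1 contains a calculation error.** With no effect size given, neither can be shown. This is a mismatch between sections, not wrong arithmetic.
- **That the sponsor will choose the test after seeing outcomes.** Section 3.4 provides for unblinded summaries about every 12 months, at the request of regulatory agencies and for internal and regulatory use. Nothing there links them to the choice of test. It is a reason to keep a record and no more.
- **That every intra-operative screen failure is left out of the primary analysis.** Section 2.2 says this only of patients whose fascia cannot be fully closed. The withdrawals for defect size (5.2.1) and active infection (6.2.1) carry no such statement.

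**Conclusion.** The mismatch is certain on the text: 80% power is stated for a log-rank test, and the statistical plan contains no such analysis and names no primary test. Followed as written, the plan leads to Fisher's exact test, although that is an inference from the form of the endpoint. The stated power then belongs to a different analysis.

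The size is moderate and conditional. Under the assumptions listed, Fisher has about 70 to 76% power where log-rank has about 80%. That is mostly conservatism, and it moves the detectable rate by only about 1 to 3 percentage points. The larger loss is that no reader can check the 80% or know what difference it refers to. It should be fixed before the analysis; it does not invalidate the design.

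**What to change.** In Section 3.2, name as primary the test that 3.1 already uses:
- a two-sided 5% log-rank comparison of time to true recurrence, with patients lost before 1 year censored at their last assessment;
- Kaplan-Meier 1-year recurrence by arm, and the difference with a 95% confidence interval;
- Fisher's exact test as a sensitivity analysis.

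State whether a recurrence first found at a Visit 7 held after day 365, but inside its +28-day window (6.7), counts as within 1 year. State how the analysis treats deaths and investigator withdrawals (5.3.3).

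If Fisher is kept as primary instead, restate the power for Fisher and say how patients without 12-month status are counted.

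In either case:
- in 3.1, give the sponsor's assumed 12-month rates, the horizon in months, the dropout, and the difference that 60 per arm detects at 80% power;
- change the significance level in 3.1 from 95% to 5%, and the number of groups in 3.2 from four to two;
- reconcile the intention-to-treat statement with the Section 2.2 exclusion of patients whose fascia cannot be closed, and give the power for the number analysed;
- record whether those making the change had seen any unblinded summary under 3.4.

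The cost is an amendment with ethics approval (11.6). No patients, visits or data are added. The stated power may become less favourable, and censoring assumes that dropout is unrelated to recurrence risk.

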#### 3.2 Statistical Plan

Given the 1:1 randomized nature of the clinical trial and to preserve the inherent characteristics of the randomization, analysis by intention-to-treat (ITT) is chosen. This type of analysis compares the study groups in terms of the treatment to which they were randomly allocated, irrespective of the treatment they actually received or other trial outcomes. Regardless of protocol deviations and participant compliance or withdrawal, analysis is performed according to the assigned treatment group. This type of analysis will also help to demonstrate if there is superiority of one mesh over the other.

If there is no superiority of one mesh over the other, analysis will be performed using the same outcomes to assess if there is equivalence between both meshes. This will demonstrate that there is no clinically significant difference between the two treatment arms.

For statistical analysis, these outcomes can be classified into two measurement scales- continuous and categorical. For continuous outcome, mean and standard deviation, median and range for each group will be calculated. ANOVA will be used to compare the difference in the means among the two groups when data are reasonably normally distributed. Otherwise, non-parametric ANOVA will be used. For categorical data, proportion will be obtained for each outcome, along with 95% CI derived from exact method. Difference in the proportions among the four groups will be compared using Fisher's exact test.

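### Section 3.2 does not say how the expected 15–20% of patients without a 12-month outcome enter the primary recurrence comparison, and the only method it names, a simple proportion, handles them poorly

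*Combined protocol and SAP*

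**What the plan says.** - Section 2.4.1 defines the primary comparison: "The primary objective of this study is to compare the incidence of true hernia recurrence", at or before 1 year, between the two arms.
- Section 3.2 fixes the analysis group: "Regardless of protocol deviations and participant compliance or withdrawal, analysis is performed according to the assigned treatment group". Section 3.3 repeats this.
- Section 3.2 also gives the method for a binary outcome: "For categorical data, proportion will be obtained for each outcome, along with 95% CI derived from exact method". Fisher's exact test compares the arms. No denominator is defined.
- Section 3.1 gives the size, "A total of 120 patients, 60 Strattice and 60 Fortiva patients will be enrolled", and the expected loss: "The analysis also contemplates a 15 to 20% dropout rate for the primary outcome".
- Section 3.1 gives the design basis: "Power analysis and sample size determination is based on Log-rank test for equality of recurrence rates over time during the study between groups". It mentions Kaplan-Meier curves as a source of hazard rates. Section 3.2 names neither method as an analysis.
- Section 5.3.3 lets the investigator withdraw a patient for a serious AE or for developing a condition on the exclusion list. Data already collected are kept, but no rule covers the missing 12-month outcome.

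**The concern.** A proportion needs a yes or no for everyone in its denominator. With 18–24 outcomes expected to be unknown, someone must decide whether those patients stay in the denominator and, if so, with what outcome. The plan leaves this open. Several choices fit the text and they give different answers, so the choice could be made after the data are seen.

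Neither way of forming the stated proportion uses the time a patient was known to be free of recurrence before leaving, and no sensitivity analysis is planned. The stake is larger because 3.2 moves on to an equivalence assessment, without a stated margin, if superiority is not shown. Any handling that pulls the risk difference toward zero would favour that conclusion.

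**Working it through.** **The plan's own figures.** 15–20% of 120 is 18–24 patients, or 9–12 per arm of 60, leaving 51–48 per arm with an outcome. The claim that "This sample size will give the study a 95% significance level and 80% power" cannot be reproduced, because no hazard rate, recurrence rate or difference is stated.

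**Assumptions for the check (not in the plan).** True 12-month recurrence p of 30% in one arm and 15% in the other; constant hazard; recurrence found only at the 6-week and 3-, 6- and 12-month visits (sections 6.4–6.7); a fraction d of patients would leave early, for reasons unrelated to recurrence.

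**Step 1. Recurrences found before leaving.** Let F(t) = 1 − (1 − p)^t, with t in years, and let f be the share of leavers whose recurrence is found before they go.
- All leave just after 6 weeks: f = F(6/52), which is 0.040 for p = 0.30 and 0.019 for p = 0.15.
- Leaving spread evenly over the year: f = (0.25 − 6/52)·F(6/52) + 0.25·F(0.25) + 0.5·F(0.5), which is 0.108 and 0.0515.

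**Step 2. Everyone allocated in the denominator, unknown counted as no event.** Reported rate = (1 − d)p + d·f. With d = 0.20:
- p = 0.30: 0.24 + 0.20 × 0.040 = 0.248, or 0.24 + 0.20 × 0.108 = 0.262.
- p = 0.15: 0.12 + 0.20 × 0.019 = 0.124, or 0.12 + 0.20 × 0.0515 = 0.130.

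The true 15-point difference is reported as about 12–13 points.

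**Step 3. Known outcomes only.** Reported rate = [(1 − d)p + d·f] / [(1 − d) + d·f]. For p = 0.30 and d = 0.20: 0.248/0.808 = 0.307, or 0.262/0.822 = 0.319. Early recurrences stay in while recurrence-free leavers drop out, so the rate is slightly too high.

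**Step 4. Kaplan-Meier by assigned arm.** The estimate is 1 − Π(1 − h), where h at each visit is the share of patients examined there, and recurrence-free until then, who have recurred. If leaving is unrelated to recurrence, each h is right and the product equals 1 − p. The estimate returns 30.0% and 15.0% under both dropout patterns.

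**Step 5. Unequal dropout under the Step 2 rule.**
- 30% lost in the 30% arm and 10% in the 15% arm: 0.21 + 0.30 × (0.040 to 0.108) is about 22–24%, against 0.135 + 0.10 × (0.019 to 0.0515), about 14%. The 15-point gap becomes about 8–10.
- True 30% in both arms, 10% vs 25% lost before any recurrence is seen: 0.90 × 30% = 27.0% against 0.75 × 30% = 22.5%. A difference of 4.5 points appears where none exists, and Fisher's test rejects in 5.7% of trials, against about 3% with equal dropout.

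**Step 6. How far the unknowns could move the result.** With 30% recurrence among completers, counting all unknowns in an arm as free or all as recurred gives 25.5–40.5% at d = 15% and 24.0–44.0% at d = 20%. The between-arm difference can move by up to 15–20 points. For scale, 60 per arm with complete data gives 80% power (two proportions, two-sided 0.05 assumed) for 30% vs 9.7%, a gap of about 20 points.

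**The case against.** A reader might infer that the plan counts dropouts as recurrence-free and that the primary comparison is therefore biased. The documents do not support that. The intention-to-treat sentence assigns patients to arms, not outcomes to patients, and the sentence on proportions gives no denominator. Observed-case analysis is open, and censoring would fit the log-rank basis in 3.1. Nor does the plan keep every withdrawn patient: section 2.2 leaves patients whose fascia cannot be fully closed out of the primary analysis, and 5.3.4 allows replacement.

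The sizes also need limits:
- With equal true rates and equal dropout, the Step 2 rule does not bias the comparison. With equal dropout it leaves the risk ratio essentially unchanged and shrinks only the difference.
- The fall to 8–10 points needs an assumed 30% vs 10% dropout, for which the plan gives no basis.
- The two ways of forming the proportion differ little in power: 59.1% against 61.3% at an assumed 30% vs 10% with 20% dropout.
- The unknowns are about as many as the observed recurrences only near 18% recurrence, the bottom of the 18–50% background range in section 2.2.
- Kaplan-Meier censoring also assumes that leaving is unrelated to recurrence, and 5.3.3 makes that doubtful.

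All of this stands. It makes the bias conditional. It does not supply the missing rule, and it leaves 3.2 naming only the method that handles dropout worst.

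**Conclusion.** The point holds as a gap in specification together with an inferior named method. The plan expects 18–24 unknown primary outcomes and gives no denominator, censoring rule, imputation or sensitivity analysis for them. It also does not carry its log-rank design basis into the analysis.

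Under constant hazard, visit-based detection and 20% dropout unrelated to outcome, a true 30% is reported as about 25–26% over all allocated patients or 31–32% over known outcomes. Kaplan-Meier recovers 30%. Larger distortions require unequal or outcome-related dropout, which the plan neither assumes nor rules out. The point should be settled before unblinded comparison; it does not show that the trial's result will be wrong.

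**What to change.** State in 3.2 that:
1. The primary analysis is by assigned arm, using the Kaplan-Meier estimate of 12-month recurrence per arm and its difference with a 95% CI, with the log-rank test that 3.1 already assumes.
2. Patients who leave without recurrence are censored at their last examination for recurrence and are not counted as recurrence-free at 12 months.
3. Time is taken on the scheduled-visit scale, so that an examination late in the ±28-day window of section 6.7 counts as the 12-month examination.

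Because withdrawals under 5.3.3 may be related to outcome, add one pre-specified tipping-point table. It should vary the number of recurrences among the unknown outcomes separately in each arm and show where the conclusion changes.

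The cost is SAP wording and one extra table from examinations already scheduled. The interval will be slightly wider. No visit or treatment changes.

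### A non-significant superiority result leads to an equivalence claim with no margin, equivalence test or confidence-interval rule

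*Combined protocol and SAP*

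**What the plan says.** Section 2.4.1 sets the primary objective: to "compare the incidence of true hernia recurrence" at or before 1 year between the Fortiva and Strattice groups.

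Section 3.2 says that if superiority is not found, "analysis will be performed using the same outcomes to assess if there is equivalence between both meshes". The next sentence is "This will demonstrate that there is no clinically significant difference between the two treatment arms". Section 3.3 repeats both sentences, with only the word for the device changed: "analysis will be performed using the same outcomes to assess if there is equivalence between both implants".

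On methods, section 3.2 says "these outcomes can be classified into two measurement scales- continuous and categorical". For continuous outcomes, "ANOVA will be used to compare the difference in the means among the two groups", with a non-parametric version if normality fails. Differences in proportions "will be compared using Fisher's exact test". The one confidence interval mentioned is an exact 95% interval for each outcome's proportion. It is not an interval for the difference between arms and is tied to no decision.

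Section 3.1 says: "Power analysis and sample size determination is based on Log-rank test for equality of recurrence rates over time". It gives 60 patients per arm, 80% power and 15 to 20% dropout, but no recurrence rate, hazard ratio or margin.

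**The concern.** A test of difference that fails to reach significance shows only that the data do not exclude zero. To show equivalence, the data must exclude every difference large enough to matter, which requires a stated margin and a rule for judging the interval against it. The plan has neither, and it does not define a clinically significant difference. Anyone following it would have to choose the criterion after seeing the results, or treat the non-significant test as the answer.

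The primary comparison is at stake. A trial of this size could miss a large difference in recurrence and then report, in the plan's own words, that no clinically significant difference exists. The equivalence step also covers all of the outcomes, so the same claim could be made for any secondary endpoint. Section 3.4 adds to the risk: unblinded summaries go to the sponsor, which makes one of the implants, about every 12 months.

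**Working it through.** **Inputs from the documents.** Section 3.1: 60 per arm, 1:1 allocation, 80% power, 15 to 20% dropout. At 20% dropout, 60 × 0.80 = 48 per arm. Section 5.3.4 allows replacements, so 48 is one scenario. The documents give no expected rate and no margin, so every rate and margin below is an assumption.

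**The plan's own figure.** The 120 patients cannot be reproduced, because no hazard rate is given. Solving backwards (Schoenfeld, two-sided 0.05, 80% power, 60 per arm), the number fits 18% vs 4.1% (hazard ratio 0.21), 30% vs 10.6% (0.315) or 50% vs 25.8% (0.43). It is not called wrong here. It is a sample size for detecting a difference.

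**Two results that would enter the equivalence branch.** The Newcombe interval for d = p2 − p1 uses the Wilson limits (l, u) of each arm: lower = d − √[(p2 − l2)² + (u1 − p1)²]; upper = d + √[(u2 − p2)² + (p1 − l1)²].

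- 12/60 vs 21/60: Wilson 95% limits are 0.118 to 0.318 and 0.242 to 0.476, and d = 0.15. Lower = 0.15 − √(0.108² + 0.118²) = −0.010. Upper = 0.15 + √(0.126² + 0.082²) = 0.300. Fisher p = 0.101. (The Wald interval is −0.008 to 0.308.)
- 3/60 vs 9/60, a threefold difference: Wilson 95% limits are 0.017 to 0.137 and 0.081 to 0.261, and d = 0.10. Lower = 0.10 − √(0.069² + 0.087²) = −0.011. Upper = 0.10 + √(0.111² + 0.033²) = 0.216. Fisher p = 0.125.

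In both cases superiority is not shown, yet the data are compatible with differences above 20 points.

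**Chance of entering the branch when the true difference is 15 points.** For Fisher, the binomial probabilities P(x)P(y) were summed exactly over all tables that are non-significant at two-sided 0.05. For log-rank: simulation, exponential times, censoring at 12 months, 20,000 runs.

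| True 12-month rates | Fisher, n = 48 | Fisher, n = 60 | Log-rank, n = 48 | Log-rank, n = 60 |
|---|---|---|---|---|
| 20% vs 35% | 70% | 62% | 62% | 55% |
| 10% vs 25% | 61% | 51% | 50% | 41% |
| 5% vs 20% | 52% | 37% | 36% | 27% |

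These are chances of reaching the equivalence step. They are not false-equivalence rates, which cannot be defined without a criterion.

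**Could the trial show equivalence properly?** Power when the true rates are equal and the rule is that the two-sided 90% Newcombe interval lies wholly inside ±margin (exact enumeration, n = 48 / n = 60):

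| Common rate | Margin 10 points | Margin 15 points |
|---|---|---|
| 2% | 73% / 83% | 98% / 99% |
| 5% | 32% / 45% | 80% / 91% |
| 10% | 4% / 13% | 50% / 68% |
| 18% | below 1% | 23% / 40% |

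A normal-approximation check on the last row, using two one-sided tests at 0.05 with 80% power: n per arm = 2p(1 − p)(1.645 + 1.282)²/m² = 2 × 0.18 × 0.82 × 8.564/0.10² = 253. With 60 per arm, the smallest margin supported is √(0.2952 × 8.564/60) = 0.205, or 20.5 points.

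So 60 per arm could be adequate or hopeless for equivalence, depending on two quantities that the plan does not state.

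**The case against.** The strongest reply is that the plan does not equate non-significance with equivalence. It announces a further analysis whose purpose is to find out whether equivalence holds, so the sentence that follows may describe only a favourable outcome. In both worked examples the 90% Newcombe interval excludes zero (0.016 to 0.277; 0.008 to 0.196) and its upper limit exceeds both 10 and 15 points. A conventional equivalence analysis at those margins would refuse the claim. Section 3.1 also describes the output as preliminary and benchmark data, and both devices are already cleared, so this is a fallback in a post-market study.

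The milder reading is possible, but it does not rescue the text: even then, nothing defines a favourable outcome. The examples are refused only because a margin and a rule have been supplied from outside the plan. The preliminary label lowers the stakes without giving a criterion, and the protocol foresees journal publication.

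Two cautions about the rates do stand. Section 1.1 reports no recurrences with porcine dermis, but the cited series used a product that section 1.1 elsewhere describes as cross-linked, unlike both study implants. The 18 to 50% in section 2.2 is for incisional hernia in general. Neither is an estimate of 1-year recurrence with these devices, so the tables are illustrative. Two gaps in any remedy also deserve attention: how subjects without a 12-month status are counted, and the fact that the surgeon is unblinded.

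**Conclusion.** The concern holds, and the text should be corrected before any comparative analysis. The plan states an equivalence conclusion as the outcome of a failed superiority comparison and gives no means of testing it. This rests on the wording alone and needs no assumed rate.

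The practical size does rest on assumptions. With a true 15-point difference and 12-month rates from 5% vs 20% to 20% vs 35%, the chance of reaching the equivalence branch runs from 27% (log-rank, 60 per arm) to 70% (Fisher, 48 per arm). With equal true rates, power to show equivalence within 10 points ranges from 83% at 2% recurrence to below 1% at 18% (60 per arm). The sample size is not shown to be wrong for its stated purpose.

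**What to change.** In both 3.2 and 3.3, delete the sentence claiming that no clinically significant difference will be demonstrated, and replace it with text to this effect:

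> A non-significant superiority test will by itself be reported as inconclusive, and the 12-month recurrence difference will be given with its two-sided 95% confidence interval. Equivalence will be assessed for 12-month true recurrence only. It will be concluded only if the two-sided 90% score-based interval for the difference lies wholly inside a clinically justified margin fixed before any unblinded summary is seen. If no such margin is fixed, no equivalence claim will be made. Other outcomes will be reported with estimates and intervals, without equivalence claims.

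A score-based interval is preferred because Wald is too liberal here. At true rates of 2% vs 12% with a 10-point margin, it wrongly concludes equivalence 8.4% / 9.0% of the time (48 / 60 per arm), against 4.5% / 4.2% for Newcombe.

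State in 3.1 that the sample size was not set for equivalence. Also state how subjects with no 12-month status enter the analysis, since counting them as recurrence-free could favour equivalence. Have the margin set by people who have not seen outcomes by arm. A per-protocol repeat is optional; if used, its analysis set must be consistent with the intra-operative screen-failure exclusions in 2.2, 5.2.1 and 6.2.1.

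The cost is wording in 3.1 to 3.3, with no change to sample size, visits or data collection. The sponsor must justify a margin or give up the claim, and equivalence on the other outcomes is dropped. If an unblinded annual summary under 3.4 has already been seen, the timing condition cannot be met, and the default is to report the difference with its interval and make no equivalence claim.
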